9.1.4 Exploratory Endpoints

1. TTP, RR, PFS, OS, TTF, AFP response, and toxicity and tolerability will be described in subsets defined by HBV, HCV, Asian, and non-Asian status.
2. CTC will be enumerated in peripheral blood at baseline and after 1 and 2 cycles of therapy to evaluate for any relationship between baseline levels and change in levels with median TTP and/or OS.
3. Archival tumor specimens will be sectioned for IHC testing of selected mTOR pathway markers and next-generation sequencing. Markers will be dichotomized as high or low using published cutpoints to describe incidence of activation in study population and explore for relationship to clinical outcomes including TTP and AFP response.
4. In patients with chronic active HBV and/or positive HBcAb, hepatitis B viral DNA quantitative will be monitored for rates of viremia/reactivation on study.
5. Optional patient blood specimens (including serum, PBMC, whole blood, and plasma) and left-over archival pathology specimens will be banked in the UCSF Hepatobiliary Tissue Bank (HBTB) for future research.

9.2 Determination of Sample Size and Accrual Rate

9.2.1 Sample Size and Power Estimate

The sample size for this phase II study will be 25 patients under the assumption that the time to progression is approximately exponentially distributed and patients come onto study uniformly

during the study accrual. A sample size of 25 evaluable patients will have sufficient power to detect the difference between the null hypothesis that the median TTP is less than 3 months (based on historical controls) and the alternative hypothesis that the median TTP is more than 6 months. The study will have a 1-sided significance level of 10% and a power of 88% under the exact test for comparison of the TTP rates between $p_0 < 25\%$ versus $p_1 > 50\%$ at 6 months.

A median TTP of > 6 months would constitute a meaningful outcome in advanced HCC, based upon the benchmarks of first-line TTP of 5.5 months in the SHARP study and 2.8 months in the Asia-Pacific study.(Llovet, Ricci et al. 2008; Cheng, Kang et al. 2009) If median TTP is > 6 months in this study, a randomized phase II trial to compare the combination therapy to single-agent sorafenib should be considered. Such a trial would be much larger and more costly, however, and should not be undertaken prior to the current study to confirm that there is tolerability and a signal of efficacy to warrant proceeding with the larger trial, noting in particular the challenges to accrual in first-line HCC studies historically, as faced by contemporary cooperative group studies CALGB 80802 and ECOG 1208.

Accrual of 25 paired archival tumor and blood specimens also constitutes a meaningful endpoint in that it will enable future biomarker studies in subsets of patients with radiographic response, AFP response, prolonged stable disease, and primary progression, including potential exploratory studies for association with tissue biomarkers of mTOR pathway activation (such as pS6 staining).(Villanueva, Chiang et al. 2008)

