1.3 Rationale for the Proposed Study

Despite its prominence as the third most common cause of cancer death world-wide, HCC lags far behind all other malignancies with only one systemic therapy (sorafenib) with proven benefit in advanced disease. New treatments and combinations are urgently needed in this grim disease. Based upon the emerging evidence for anti-tumor activity of mTOR inhibitors in HCC, the molecular rationale for combination of mTOR inhibition with sorafenib, and the provocative data from the UCSF-Northwestern phase I trial as reported above, a phase II study is warranted to better define the efficacy of this regimen. This protocol describes a single-arm phase II study with overall goal to confirm the signal of efficacy observed in the phase I dose-finding setting, to establish the tolerability of the regimen in a larger cohort, and to further explore potential biomarkers of response. The single-arm, one-stage design will expeditiously determine whether there is an adequate signal of efficacy and adequate tolerability to warrant a much larger and significantly more costly randomized study design with single-agent sorafenib as a control arm, noting the recent negative outcomes of multiple large randomized trials in HCC (including the second-line BRISK-PS trial of brivanib versus placebo as well as the first-line trial of sunitinib versus sorafenib), whose negative results have been attributed in part to insufficient phase II data, intolerability, and lack of robust markers of response.(BusinessWire 2011; Cheng 2011)

The hypothesis of this single-arm phase II study is that the combination of temsirolimus and sorafenib will achieve a clinically-meaningful median time to progression (TTP) of at least 6 months, with null hypothesis of less than or equal to 3 months, in first-line systemic therapy for patients with advanced HCC. A randomized trial would be required to formally compare the efficacy of this combination to sorafenib alone and will be indicated if this phase II study achieves a median TTP of at least 6 months. An interim safety analysis will employ stopping rules after 30% of planned patients have been treated with at least one dose of protocol therapy to ensure the combination does not confer excessive toxicity.

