* Patients will be followed every 3-6 months for up to 5 years after study discontinuation or until death, at standard-of-care clinic visits with treating investigator or by telephone calls from treating investigator or a designated study coordinator (± 3 months)

¹ May start study prior to obtaining specimens if pathology report is available

² Confirmation of antiviral therapy with an appropriate antiviral agent for HBV is required in patients with positive hepatitis B surface antigen, HBcAb IgM, and/or viral load

³ Sorafenib will be taken orally twice daily at starting dose with modifications per Section 5.2.3

⁴ Weight and vital signs on Days 8, 15, 22 of Cycle 2 and future cycles

⁵ Disease assessment including Child-Pugh, BCLC, and CLIP scores

⁶ Evaluation of clinical response or deterioration at Follow-Up Visit: overall survival will be measured from time of first dose of therapy to date of death, evaluation of any residual symptomatic adverse events (if applicable), other anti-cancer therapies

⁷ Complete metabolic panel (electrolytes, BUN, creatinine, glucose, calcium, magnesium, phosphorus, total and direct bilirubin, alkaline phosphatase, albumin, AST, and ALT)

⁸ Prothrombin time/ international normalized ratio (PT/INR)

⁹ Hepatitis B viral DNA quantitative in patients with positive hepatitis B viral load at baseline (Screening) and/or positive HBsAg, HBcAb total, and/or HBcAb IgM (odd cycles only or more frequently at investigator's discretion), and end of treatment if not measured within 4 weeks prior.

¹⁰ Screening and Day 1 of odd cycles only (Cycle 3, 5, 7, etc.)

¹¹ Initiate standing phosphate repletion for patients with baseline ≥ Grade 2 hypophosphatemia; adjust dosage as clinically indicated at each visit

¹² CTC on Day 1 of Cycles 1, 2 & 3 only. See Study Laboratory and Procedures Manual for instructions

¹³ Banking blood samples on Cycle 1 Day 1, Cycle 1 Day 8, and Cycle 3 Day 1, and at End of Treatment (if not done within 4 wks). See Study Laboratory and Procedures Manual for instructions

¹⁴ Odd cycles only, every 8 weeks ± 7 days, starting Cycle 3, Day 1

¹⁵ If not done within 8 weeks, imaging with CT chest (with or without contrast) plus triphasic CT abdomen and pelvis with intravenous contrast or triphasic gadolinium-enhanced MRI abdomen/pelvis

¹⁶ May use values from >28 days from registration

¹⁷ Temsirolimus infusion may be performed within ± 3 days

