9.1.2 Primary Endpoint

Median TTP will be calculated in months from date of first dose of protocol therapy to date of removal from study for radiographic (per RECIST 1.1) and/or clinical progression including death attributed to progression. For patients removed from study for other reasons than progression (such as toxicity, withdrawal of consent, or death from other causes than documented radiographic and/or clinical progression), TTP will be censored at the date last known to be progression-free.

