9.4.2 Analysis of Primary Endpoints

Kaplan-Meier methods will be used to summarize the primary endpoint (median TTP) with 95% confidence intervals. The proportion of patients with TTP equal to or exceeding 6 months will also be calculated and reported along with 95% confidence intervals.

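### The 88% power in 9.2.1 is the power to reject a 3-month median TTP, not the chance of meeting the observed 6-month median criterion, and 9.4.2 omits the powered test

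*Combined protocol and SAP*

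**What the plan says.** Section 9.2.1 sets 25 evaluable patients, assumes roughly exponential TTP, and contrasts a median below 3 months with one above 6 months. It translates these into 6-month rates of 25% and 50% and adds: "The study will have a 1-sided significance level of 10% and a power of 88% under the exact test". No number of patients is given as the cut-off.

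The criterion for going further appears twice. Section 1.3 says that a randomised trial "will be indicated if this phase II study achieves a median TTP of at least 6 months". Section 9.2.1 says: "If median TTP is > 6 months in this study, a randomized phase II trial to compare the combination therapy" with sorafenib alone should be considered. The 6-month target is justified "based upon the benchmarks of first-line TTP of 5.5 months in the SHARP study and 2.8 months in the Asia-Pacific study".

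Section 9.4.2, the primary analysis, names no test, null value or significance level. It says "Kaplan-Meier methods will be used to summarize the primary endpoint (median TTP) with 95% confidence intervals" and "The proportion of patients with TTP equal to or exceeding 6 months will also be calculated and reported along with 95% confidence intervals", without giving the interval method.

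Two further passages affect how TTP is recorded. Imaging is scheduled "Odd cycles only, every 8 weeks ± 7 days, starting Cycle 3, Day 1" (Table 6.1, footnote 14). Section 9.1.2 measures TTP "to date of removal from study for radiographic (per RECIST 1.1) and/or clinical progression including death attributed to progression" and censors patients who leave for toxicity, withdrawal or death from other causes.

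**The concern.** The trial exists to judge whether a larger and costlier randomised trial is worth running. A reader of 9.2.1 will naturally take 88% as the chance that a regimen with a true 6-month median clears the bar the protocol sets. The powered test and the stated bar are different rules. The test asks whether the 6-month rate exceeds 25%. The criterion asks whether the observed median reaches 6 months. A result can satisfy the first and miss the second, and the test is absent from the analysis section. If the result falls between the two, its meaning would have to be settled after the data are seen.

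**Working it through.** **Inputs.** n = 25, one-sided alpha 10%, 6-month rates 25% and 50%, exponential TTP (9.2.1); observed-median criterion (1.3, 9.2.1); 95% intervals (9.4.2); 8-weekly imaging (Table 6.1). Let X be the number of 25 patients progression-free at 6 months, with no censoring before then. Under the exponential model the rate at L months is p = 0.5^(L / median).

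**1. Reproduce the 88%.** At L = 6, a 3-month median gives 0.5^(6/3) = 0.25 and a 6-month median gives 0.5^(6/6) = 0.50.

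| Reject at | P(X ≥ r) at p = 0.25 | P(X ≥ r) at p = 0.50 |
|---|---|---|
| 9 | 0.149 | 0.946 |
| 10 | 0.071 | 0.885 |
| 11 | 0.030 | 0.788 |
| 12 | 0.011 | 0.655 |
| 13 | 0.003 | 0.500 |

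The smallest cut-off with alpha at or below 10% is 10, with power 88.5%. The stated figure reproduces.

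**2. The observed-median criterion.** With 25 uncensored times the Kaplan-Meier median is the 13th ordered time. It lies beyond 6 months only if at most 12 patients have progressed by then, so X ≥ 13. At a true 6-month median, P(X ≥ 13) = 0.500.

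**3. The gap.** P(10 ≤ X ≤ 12) = 0.885 − 0.500 = 0.385 at a true 6-month median. At a true 3-month median it is 0.071 − 0.003 = 0.068.

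**4. The 95% interval for the 6-month proportion, if it were used to exclude 25%.** Lower limits:

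| Method | 10/25 | 11/25 | 12/25 |
|---|---|---|---|
| Exact | 0.211 | 0.244 | 0.278 |
| Wald | 0.208 | 0.245 | 0.284 |
| Kaplan-Meier, log-log | 0.213 | 0.245 | 0.278 |
| Wilson | 0.234 | 0.267 | 0.300 |
| Kaplan-Meier, log | 0.248 | 0.283 | 0.319 |

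No method excludes 25% at 10/25. The first three need 12/25 (power 65.5%); the last two need 11/25 (78.8%). The limit that matches the test is the one-sided 90% exact lower limit: 0.230 at 9/25 and 0.265 at 10/25.

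**5. Scan-based dating.** Six months is 26.1 weeks, so the last scheduled scan before it is at week 24, or 24 × 7 / 30.4375 = 5.52 months. If progression is dated only at scans, the recorded 6-month rate is 0.5^(5.52/6) = 0.529 at a true 6-month median and 0.5^(5.52/3) = 0.279 at a true 3-month median.

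| Rule | Continuous dating | Week-24 dating |
|---|---|---|
| Exact test (≥ 10), true 6-month median | 88.5% | 93.2% |
| Exact test (≥ 10), true 3-month median (error) | 7.1% | 13.2% |
| 95% interval of proportion excludes 25% (≥ 12 or ≥ 11), true 6-month median | 65.5% or 78.8% | 75.4% or 86.2% |
| Observed-median criterion (≥ 13), true 6-month median | 50.0% | 61.4% |
| 10 to 12 of 25, true 6-month median | 38.5% | 31.8% |

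**6. Removal lag.** TTP ends at removal from study, which may follow the scan. The documents give no figure for this lag, so the values here are assumptions. With a 2-week lag, simulation at a true 6-month median gives 82% for the median criterion and 98% for the exact test (70% and 96% if 40% of progressions are clinical and dated exactly). At a true 3-month median the same lag puts P(X ≥ 10) at 37% (22% with 40% clinical). Lag therefore raises the error rate as well as the power, so 61% is not an upper bound for the median criterion.

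**The case against.** The strongest reply is that the plan's figure is right and that 9.2.1 already fixes the test, side, level, landmark, rates and sample size, from which 10 of 25 follows uniquely. That stands. What remains is that the cut-off is unwritten and that the primary analysis never carries out the test that justified 25 patients.

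A second reply is that the 95% intervals only summarise. This also stands. A reader might infer from 9.4.2 that the trial succeeds only if the 95% interval excludes 25%, and hence that its real power is 65% to 79%. The documents attach no decision to either interval. Those figures apply only if the interval of the proportion were put to that use; they do not describe the interval of the median.

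A third reply is that the criterion is soft: both sentences say if, not only if; 9.2.1 asks only that a trial be considered; and tolerability also counts. Moreover, a roughly even chance that an estimate reaches the true value is generic. Agreed, and a bar above the 3-month null is reasonable against the 5.5-month benchmark. A reader might infer that 10 to 12 of 25 counts as failure. The plan does not say so, and the criterion could be shorthand for rejecting the null. The difficulty is that it does not say that either.

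Finally, 10 to 12 is not uniform: 12 of 25 excludes 25% by every interval in the working, and 11 of 25 does so by some.

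**Conclusion.** The concern holds as a mismatch between the stated power and the stated go criterion; it does not show an error in the 88%. Under the plan's own exponential model, with continuous dating and no censoring before 6 months, a regimen with a true 6-month median rejects the null with 88.5% probability and meets the observed-median criterion with 50%. The 38.5% of such trials between the two have no stated reading. With week-24 dating throughout, the corresponding figures are 93%, 61% and 32%, and the test's error rate at a true 3-month median is 13%. Removal lag can raise the power and error figures further, but the two rules remain apart under the lags tried.

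A reader might also conclude that the go threshold should drop to 10 of 25 or that more patients are needed. Neither follows. At a true 5.5-month median with continuous dating, a threshold of 10 would raise the chance of going forward from 38% to 81%. This should be fixed, because following the stated criterion does not deliver the stated power.

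**What to change.** 1. In 9.4.2, name the one-sided 10% exact test of the 6-month TTP proportion against 25%, rejecting at 10 or more of 25. Report the matching one-sided 90% exact lower limit (26.5% at 10/25) beside the 95% interval, and state the interval method. Say how patients censored before 6 months are counted, or test the Kaplan-Meier 6-month estimate at the same level.
2. In 1.3 and 9.2.1, state that 88% is the power to reject the 3-month-median null, and that the probability of meeting the observed-median criterion at a true 6-month median is about 50% under the plan's assumptions. Note that scan-based dating and removal lag raise both this probability and the test's error rate. I would not print a table of probabilities for several true medians, since they depend on a lag the plan does not specify.
3. Use one wording for the median criterion in both sections. Then either say that rejecting the null without reaching it shows activity above the 3-month null but does not meet the go criterion, or say that the criterion means rejection of the null.

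The cost is a few sentences. On the first reading in item 3, the go threshold and sample size are unchanged; the downside is a less favourable stated probability of meeting the go criterion. The second reading would put the bar at 10 of 25, with the consequence at 5.5 months given in the verdict, so it should be chosen only if that is what the plan already means.

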9.2.2 Accrual estimates

It is estimated that 12 patients will be accrued annually (approximately 1 patient per month) combined between UCSF and Northwestern. This estimate is based upon the accrual to the predecessor Phase I study of this combination which enrolled 25 patients with similar eligibility criteria between December 2009 and April 2012. It is expected that the Phase II study will accrue faster than the Phase I due to the established infrastructure and momentum from the Phase I study, along with no requirement for delays for dose escalation and frequent amendments which were associated with the Phase I study.

9.3 Interim Analyses and Stopping Rules

No interim assessment for primary endpoint is planned, but there will be a planned interim safety analysis by the UCSF Data and Safety Monitoring Board after the first 30% of the planned study participants (8 patients) have enrolled and completed at least one cycle of protocol therapy or been removed for toxicity. Study accrual will not be interrupted for the early safety assessment. The proportion of patients with treatment-related adverse events of grade 3 or higher and/or an unacceptable toxicity event (with exceptions defined in Section 6.4) will be summarized with 90% two-sided exact confidence intervals. Each confidence interval will be no wider than ± 0.17 . If the lower confidence bound (LCB) exceeds 0.17, adverse events will be evaluated and a decision will be made whether to amend the protocol or close the study.

If the true rate of treatment-related toxicity is 25%, the probability that 3 or more patients will have adverse events of grade 3 or greater is 32%. A summary of probabilities for a range of true toxicity rates is shown below. If 3 or more patients among the first 8 experience an eligible grade 3 or higher and/or unacceptable toxicity event, a decision will be made whether to amend the study or close the study due to toxicity.

True Toxicity Rate	Probability 3 or more of 8 patients experience AEs of grade 3 or greater	Probability 2 or more of 8 patients experience AEs of grade 3 or greater	Probability 1 or more of 8 patients experience AEs of grade 3 or greater
---------------------------	---	---	---

10%	3.8%	18.7%	57%
20%	20.3%	50.0%	83%
25%	32.0%	63.3%	89%
30%	44.8%	74.5%	94%

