8.4 Adverse Events Monitoring

All adverse events, whether or not unexpected, and whether or not considered to be associated with the use of the study drug, will be entered into OnCore[®], as noted above.

The Investigator will assess all adverse events and determine reportability requirements to the UCSF Data and Safety Monitoring Committee (DSMC) and UCSF’s Institutional Review Board, the Committee on Human Research (CHR); and, when the study is conducted under an Investigational New Drug Application (IND), to the Food and Drug Administration (FDA) if it meets the FDA reporting criteria.

All adverse events entered into OnCore[®] will be reviewed by the Helen Diller Family Comprehensive Cancer Center Site Committee on a weekly basis. The Site Committee will review and discuss at each weekly meeting the selected toxicity, the toxicity grade, and the attribution of relationship of the adverse event to the administration of the study drug(s).

In addition, all adverse events and suspected adverse reactions considered “serious,” entered into OnCore[®] will be reviewed and monitored by the Data and Safety Monitoring Committee on an ongoing basis, discussed at DSMC meetings which take place every six (6) weeks.

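### The two triggers for the 8-patient safety decision do not match (3 or more of 8, against a lower bound above 0.17 that needs 4 of 8), and the stated ±0.17 precision is wrong for 1 to 7 events

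*Combined protocol and SAP*

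**What the plan says.** Sections 6.4 (Stopping Rules) and 9.3 (Interim Analyses and Stopping Rules) describe the same single safety analysis, in almost the same words.

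- **Timing (9.3).** It takes place "after the first 30% of the planned study participants (8 patients) have enrolled and completed at least one cycle", or have been removed for toxicity. Section 1.3 instead places it "after 30% of planned patients have been treated with at least one dose of protocol therapy".
- **Interval.** The proportion of patients with an eligible event "will be summarized with 90% two-sided exact confidence intervals".
- **Precision.** "Each confidence interval will be no wider than" ±0.17.
- **Trigger A.** "If the lower confidence bound (LCB) exceeds 0.17, adverse events will be evaluated and a decision will be made" on amending or closing.
- **Trigger B.** "If 3 or more patients among the first 8 experience an eligible grade 3 or higher and/or unacceptable toxicity event", the same amend-or-close decision follows.
- **Operating characteristics.** At a true rate of 25%, "the probability that 3 or more patients will have adverse events of grade 3 or greater is 32"%. A table gives the chance of 3 or more, 2 or more and 1 or more of 8 at true rates of 10%, 20%, 25% and 30%. It has no column for 4 or more.

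Section 8.4 adds weekly Site Committee review of adverse events, and committee review of serious events "discussed at DSMC meetings which take place every six (6) weeks". Neither has a numeric threshold.

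**The concern.** A trigger on the lower confidence bound and a trigger on the event count are two ways of writing the same kind of rule. With the sample size and interval method fixed, each bound threshold corresponds to one count. If the two counts differ, the plan has two thresholds for one decision and does not rank them.

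This is the only toxicity review in the protocol with a numeric trigger, so the committee relies on this text to know when a decision is due. The precision statement is a separate matter. With 8 patients, a 90% exact interval as narrow as ±0.17 is not plausible for most outcomes. A committee that took the figure at face value would think the observed rate much better determined than it is.

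**Working it through.** **Inputs, all from sections 6.4 and 9.3:** n = 8; 90% two-sided exact interval (5% in each tail); bound threshold 0.17; count threshold 3; true rates 10%, 20%, 25% and 30%.

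**Step 1: reproduce the plan's table.** P(X ≥ r) for X ~ Binomial(8, p):

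| True rate | 3 or more | 2 or more | 1 or more |
|---|---|---|---|
| 10% | 3.8% | 18.7% | 57% |
| 20% | 20.3% | 49.7% (printed 50.0%) | 83% |
| 25% | 32.1% (printed 32.0%) | 63.3% | 90% (printed 89%) |
| 30% | 44.8% | 74.5% | 94% |

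The table reproduces apart from the three small differences shown.

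**Step 2: exact intervals at n = 8.** The lower bound L for x events solves P(X ≥ x | p = L) = 0.05. The upper bound U solves P(X ≤ x | p = U) = 0.05. The half-width is (U − L)/2.

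| Events | Lower | Upper | Half-width |
|---|---|---|---|
| 0 | 0 | 0.312 | 0.156 |
| 1 | 0.006 | 0.471 | 0.232 |
| 2 | 0.046 | 0.600 | 0.277 |
| 3 | 0.111 | 0.711 | 0.300 |
| 4 | 0.193 | 0.807 | 0.307 |
| 5 | 0.289 | 0.889 | 0.300 |
| 6 | 0.400 | 0.954 | 0.277 |
| 7 | 0.529 | 0.994 | 0.232 |
| 8 | 0.688 | 1 | 0.156 |

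**Step 3: compare the triggers.** The lower bound is 0.111 at 3 of 8, below 0.17, and 0.193 at 4 of 8, above it. Trigger A therefore means 4 or more, and trigger B means 3 or more.

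Rounding or choice of method does not explain the gap:

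- P(X ≥ 3 | p = 0.17) = 0.141. The lower bound at 3 of 8 would reach 0.17 only at a two-sided level of 1 − 2 × 0.141 = 0.718, about 72% instead of 90%.
- Other methods at 3 of 8 give lower bounds of 0.093 (Wald), 0.137 (mid-p), 0.147 (Blaker), 0.147 (one-sided 10% exact) and 0.161 (Wilson). All are below 0.17.
- For a bound rule to mean 3 or more of 8, its threshold would have to be at least 0.046 and below 0.111.

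**Step 4: size of the mismatch.**

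| True rate | 3 or more | 4 or more | Exactly 3 (difference) |
|---|---|---|---|
| 10% | 3.8% | 0.5% | 3.3% |
| 20% | 20.3% | 5.6% | 14.7% |
| 25% | 32.1% | 11.4% | 20.8% |
| 30% | 44.8% | 19.4% | 25.4% |

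**Step 5: the ±0.17 statement.** From step 2, a half-width of 0.17 or less occurs only at 0 of 8 and 8 of 8 (0.156). For 1 to 7 events it is 0.232 to 0.307. The probability of 1 to 7 events is 57%, 83%, 90% and 94% at the four true rates. The stated figure is 0.17/0.307 = 0.55 of the largest half-width, an understatement of about 45%.

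Half-width is the lenient reading. Measured as the larger distance from the point estimate, the interval extends 0.307 to 0.350, depending on the outcome, so ±0.17 fails at every count, including 0 and 8.

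**Step 6: a possible origin.** The largest 90% exact half-width is 0.177 at n = 25, 0.173 at n = 26, 0.170 at n = 27 and 0.167 at n = 28. Section 3.2 gives 25 evaluable patients and a maximum of 28. The figure fits the whole trial and not the interim analysis. That it was carried over is an inference; the documents do not say so.

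**The case against.** The strongest reply is that the two sentences are redundant and do not contradict each other. Both are one-way conditions, and nothing tells the committee to continue when the bound is 0.17 or less. Followed together, they give one answer at every outcome: decide at 3 or more. The count rule is also the one illustrated in words and matched by a table column.

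That is the natural literal reading, and on it the bound condition never adds an outcome. But the text does not state that reading. The bound condition comes first, is tied to the specified interval, and can fairly be taken as the formal rule, in which case the table omits the relevant column.

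A second reply is that the bound sentence, like ±0.17, may belong to the full cohort: at n = 25 the exact lower bound first exceeds 0.17 at 8 of 25 (0.1703). That is possible, but the sentence stands in the paragraph on the 8-patient analysis, and the remedy would still be to correct that paragraph.

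The reply on consequence has force. Both conditions lead to a discretionary decision, accrual is not paused, and the committee will see the actual interval. The probabilities for exactly 3 of 8 show how often the ambiguity would arise, not how often a wrong decision would follow. None of this makes the precision statement correct.

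**Conclusion.** The point holds and should be fixed. Under the plan's own interval, a lower bound above 0.17 means 4 or more of 8, while the count condition says 3 or more, and the text does not say how they combine. The effect is confined to exactly 3 of 8 (3.3% to 25.4% across the plan's true rates). Depending on the reading, the chance of triggering at a true rate of 25% is 32.1% or 11.4%.

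The ±0.17 statement is wrong for 1 to 7 events however the triggers are read; the largest half-width is 0.307. The results assume exactly 8 patients with independent events at a common rate, and the Clopper-Pearson interval for the word exact. The trigger mismatch also persists under the other methods tried. This review takes no view on which threshold is right.

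**What to change.** In sections 6.4 and 9.3, reconcile the two conditions. Either define one trigger, or state that either suffices and that the bound condition is met only at 4 or more of 8. The choice is the sponsor's.

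Make the table match. The present 3-or-more column serves the count or either-condition reading. If the bound governs, add a 4-or-more column (0.5%, 5.6%, 11.4%, 19.4%).

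Replace ±0.17 with a half-width of up to 0.31 with 8 patients, worded as a half-width because exact intervals are not symmetric about the estimate, or print the nine intervals.

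While editing the table, correct three cells: 1 or more at 25% (90%, printed 89%), 2 or more at 20% (49.7%, printed 50.0%) and 3 or more at 25% (32.1%, printed 32.0%). As a minor matter, align the timing in section 1.3 (one dose) with 6.4 and 9.3 (one cycle, or removed for toxicity).

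The cost is wording and table edits in two sections and one phrase in 1.3. The stated precision becomes less favourable, and if the bound is chosen as governing, the stated chance of triggering falls.
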